## 8.6 SAFETY OVERSIGHT

Safety oversight will be under the direction of a DSMB composed of individuals with the appropriate expertise as determined by their regulatory guidelines. The DSMB will meet every 6 months to assess safety and efficacy data in each condition of the study. The DSMB will operate under the rules of an approved charter that will be written and reviewed at the organizational meeting of the DSMB. At this time, each data element that the DSMB needs to assess will be clearly defined. The DSMB will provide its input as required to NIMH.

## 9 CLINICAL MONITORING

Clinical site monitoring is conducted to ensure that the rights and well-being of human subjects are protected, that the reported trial data are accurate, complete, and verifiable, and that the conduct of the trial is in compliance with the currently approved protocol/amendment(s), with GCP, and with applicable regulatory requirement(s).

- [name], the project manager, will be responsible for the adequate clinical documentation of all events as described in the current protocol, including data verification and backup.
- Evaluation of the safety of the study will take place via the DSMB every six months and as needed when AEs emerge (see sections above).

## 10 STATISTICAL CONSIDERATIONS

### 10.1 STATISTICAL AND ANALYTICAL PLANS

There will be no formal SAP. The PI will conduct all analyses at the end of the trial.

### 10.2 STATISTICAL HYPOTHESES

**Hypotheses.** For suicidal desire and suicidal action capacity—our primary endpoints (see far right side of figure in Figure at right)—we predict that perimenstrual increases in suicidal desire and action capacity (Lab 2 – Lab 1 within each condition) will be larger in the placebo condition than in the experimental hormone stabilization condition. The associated null hypothesis is that there will be no difference in the perimenstrual increase in suicidality across condition. For our secondary endpoints, including hopelessness, negative social appraisals, reduced inhibitory control, and threat sensitivity, we predict the same pattern of results.

[figure not shown]

Figure 1. Pathophysiological Model of Increased Perimenstrual Suicide Risk

There are no “efficacy” endpoints in the present trial since it is mechanistic and not a treatment study.

### 10.3 ANALYSIS DATASETS

An intent-to-treat dataset will be utilized. The study statistician will use a carry-forward approach to evaluate the within-person condition effect using this intent-to-treat sample.

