**Assessment of Outcomes.** Participants will complete phone measures of symptoms and suicidality starting on the first day of patches/pills and ending 5 days following the last patch/pill (phone symbols in figure above). Three lab sessions will measure mediating constructs using behavioral tasks. In each condition, lab visits will occur on days +7, +14, and +22 following ovulation.

**Primary Windows of Comparison for Hypothesis Testing.** To test whether prevention of E2/P4 withdrawal is associated with mediating behavioral constructs and suicide risk, we will compare tasks and interviews in **LABPL2** with **LABEXP2**.

**Blinding of Participants and Staff.** All study staff performing assessments will remain blinded to condition. The natural within-woman variation in menstrual cycle length from one cycle to another will help maintain the participant blind. Few women have regular 28 day cycles, and between-cycle variation up to 8 days is normal. Demand characteristics regarding the impact of hormonal manipulation will be minimized by informing participants that women vary a great deal in their responses to hormones, and our current evidence does not allow us to predict for certain whether hormones have a positive, negative, or neutral effect on women's symptoms (of note, this is scientifically accurate). Finally, although some women may become unblinded later in the extended hormone phase, work by the mentoring team suggests that pharmacologic delay of menses does not influence the course of perimenstrual mood symptoms.

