**Daily Telephone Symptom Measures (PRIMARY AND SECONDARY ENDPOINTS): Depressive Symptoms and Hopelessness** using the 10-item short form of the CES-D and the Beck Hopelessness Scale, **Anxiety Symptoms** (reflecting Threat Sensitivity) using the 6-item short form of the Patient-Reported Outcome Measurement Information System (PROMIS) Anxiety scale; **Impulsive Symptoms** using a five item version of the UPPS-P Lack of Premeditation (i.e., classic impulsivity) subscale; and **Rejection Sensitivity Symptoms** (reflecting social appraisals) using two items with high item-total correlations from the Social Evaluation subscale of the State Self-Esteem Scale. *Each of these inventories has been extensively validated for the measurement of the target construct.* **Suicidal desire and action capacity** will be measured daily using a shortened version of the SITBI.

**Participant Safety:** Emergent changes in suicidality will be managed using the structured University of Washington Risk Assessment and Management Protocol (UWRAP), a safety protocol recommended by NIMH for RCTs since it allows for the safe study of individuals with suicidality. If imminent risk for suicide emerges and cannot be satisfactorily managed by the UWRAP protocol (as determined by [name]), the protocol for discontinuation will be followed. **However, because the manipulation mimics luteal E2/P4 levels that**

women naturally experience, the hormonal manipulation is not expected to pose greater risk than a normal menstrual cycle—the risk will simply be shifted in the stabilization condition.

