#### 7.3.2 ENROLLMENT/BASELINE

Following recruitment screening via telephone, interested individuals will schedule and attend an enrollment visit at which they will provide informed consent and be further assessed for eligibility; assessment for eligibility includes assessment of height and weight (BMI), urine HcG pregnancy test, consent to contact their mental health provider at appropriate intervals for study participation, and other self-reported inclusion/exclusion criteria (including appropriate level of suicide risk on the SITBI-- see information in section 5.1). If ineligible, they will be referred back to their mental health provider and receive payment for the enrollment visit. If eligibility is confirmed, they will be further characterized using the SCID-I and SCID-II and complete various psychosocial questionnaires. In addition, they will be trained in the protocol for urine ovulation testing, daily telephone assessments, and the patch/pill administration schedule. Participants will be randomized to one of two possible condition orders at that time.

Pregnancy test must be negative in order for the participant to continue with the study. The study agent will not be administered until Lab assessment 1 (i.e., not at baseline/enrollment).

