#### 10.4.2 ANALYSIS OF THE PRIMARY EFFICACY ENDPOINT(S)

Primary and secondary endpoints are operationalized above (i.e., mean within-person differences between placebo and experimental in final seven days of manipulation) for the daily SITB suicidal ideation and planning subscales (primary endpoints) as well as the daily UPPS-P impulsivity, PROMIS anxiety, CESD depression, BHI hopelessness, and SSES rejection sensitivity subscales (secondary endpoints).

**Analyses will proceed identically for all outcomes listed above.** First, we will calculate each subject's mean daily rating (via phone) on the outcome measure *in the final seven days of both the placebo condition* (placebo mean score) and the experimental condition (experimental mean score).

Second, we will utilize paired samples t-tests to examine the within-person condition effect. If proposed covariates (medicines, BMI, age) show sufficient variability, we will instead use a repeated measures ANCOVA to evaluate the condition effect. These analyses will be conducted on the intent-to-treat dataset.

If necessary due to violations of model assumptions, we will utilize similar nonparametric tests.

---

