### 10.5 SAMPLE SIZE

An unlimited number of women will be screened. 45 women will be enrolled in the study, with the goal of 30 women completing the study.

Power analyses are described below; alpha is set at .05, power at 80%. The null hypothesis is no link between the study experimental condition and risk for suicidal ideation, intent, and planning; the alternate hypothesis is that hormone stabilization in the experimental condition will prevent flux in these suicide-related outcomes. Because no previous studies have examined the impact of experimental hormones on suicidality, we have conducted power analyses using existing effect sizes on related constructs (e.g., BPD features).

**Power Analysis.** For the contrast testing the primary hypothesis, we will have power to detect a conventionally medium-sized effect of hormone withdrawal ( $r = .30$ ;  $d = .60$ ) at 80% power with just 17 participants. The PI's previous work in women with BPD suggests that attrition could be as high as 25% across two conditions; should attrition be this high, enrollment of 22 participants would be required for adequate power. However, to improve generalizability of our findings and to ensure 80% power to detect small-to-medium effect sizes ( $r = .20$ ;  $d = .40$ ), we aim to include 30 completers (with 45 women randomized). This number is especially reasonable given the

much larger effects found in the candidate's recent studies for the effect of natural ovarian steroid changes (average  $r = .58$ ;  $d = 1.38$ ) on daily symptoms of depression, rejection sensitivity, anxiety, and impulsivity.

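### The undefined carry-forward rule puts substituted ratings into the paired primary test; if condition-1 means are copied, a .40 SD difference becomes .30 SD at the cited 25% attrition and .27 SD in the upper case

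*Combined protocol and SAP*

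**What the plan says.** Section 10.3 gives one rule for missing data: "The study statistician will use a carry-forward approach to evaluate the within-person condition effect using this intent-to-treat sample". It does not say whether a daily rating, a seven-day mean or a lab value is carried, from which day, or whether a value may pass from one condition to the other.

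Section 10.4.2 forms each woman's mean daily rating over the final seven days of each condition, compares the two means with a paired t-test (or a repeated-measures ANCOVA, or a nonparametric equivalent), and adds: "These analyses will be conducted on the intent-to-treat dataset". The same steps apply to both primary and all five secondary endpoints.

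Section 10.1 states: "There will be no formal SAP". Section 10.5 plans for substantial loss: "we aim to include 30 completers (with 45 women randomized", and elsewhere says that "attrition could be as high as 25% across two conditions".

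Section 6.1.9 says that all treated days will enter multilevel models that cope with missing data. It does not say whether this is the primary analysis or a separate one.

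**The concern.** A paired test needs two values per woman. In a crossover, a woman who leaves after the first condition carries almost no information on the within-person difference. Carry-forward keeps her in the test by manufacturing that difference. In practice the only material to carry is her condition-1 daily ratings: the enrolment SITBI is the full interview (Section 7.1.1), whereas the outcome "will be measured daily using a shortened version of the SITBI".

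The endpoints in Section 4.2.1 are mean within-person differences, so the size of the estimate is the primary result, not just its p-value. Missingness may also depend on the outcome, because Section 5.4.2 removes women judged at imminent risk.

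**Working it through.** **Inputs.** 45 randomised, 30 completers, attrition up to 25%, d = .40, two-sided alpha .05 (Sections 10.4.1 and 10.5). Assumed: d is the mean difference divided by the SD of the paired difference, so that SD is 1.

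**The plan's own figure.** Section 10.5 claims 80% power for d = .40 with 30 completers. On the assumed scale the noncentral t gives 56%, and 80% needs 52 women. If d is on the raw-score SD with a within-person correlation of about .7 (also an assumption), 32 women are needed, close to 30. The scale is therefore uncertain. That is a separate issue and does not affect the shrinkage fraction below.

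**Condition-1 mean copied.** Each copied woman contributes a difference of exactly 0. With n completers, k copied women and w = n/(n + k):

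- mean difference = .40w
- SD of the filled differences = √(w + w(1 − w) × .40²)
- paired d on the filled data = mean / SD

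*25% attrition.* 25% of 45 is 11, leaving 34 completers, so w = 34/45.
- Mean = .40 × 34/45 = .302.
- SD = .886.
- Paired d = .302/.886 = .34 (average sample value in simulation about .35).

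*Upper case.* All 15 non-completers have a full condition-1 window and no condition-2 ratings, so w = 30/45.
- Mean = .40 × 30/45 = .267.
- SD = .838.
- Paired d = .267/.838 = .32.

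**Why the test hardly changes.** Mean and standard error shrink together. In the upper case the expected t is about .267/(.838/√45) = 2.14, against .40 × √30 = 2.19 for completers alone. With 11 copied it is 2.29 against .40 × √34 = 2.33.

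**Simulation of the same set-up (40,000 runs or more).**

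| | Mean difference | 95% interval covers .40 | Power | Type I error |
|---|---|---|---|---|
| 30 completers only | .40 | 95% | 56% | 5% |
| 30 + 15 copied | .27 | 81% | 56% | 5% |
| 34 + 11 copied | .30 | about 88% | 62% | 5% |

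Power with 34 completers and no copies is also 62%. In the upper case the half-width falls from .37 to .25, although no information has been added.

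**Fewer women may be affected.** Randomisation happens at enrolment ("Participants will be randomized to one of two possible condition orders at that time"), before ovulation testing and the first call. Women lost in that gap have no daily rating to carry. With 30 completers and only 5 or 8 copied women, the estimate is .34 or .32 and coverage 94% or 91%.

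**Last rating carried instead.** The result now depends on the day, because calls run "starting on the first day of patches/pills and ending 5 days following the last patch/pill". These figures are illustrations on assumed symptom courses:
- Last treatment-day rating copied across for 15 women, ratings assumed to rise during treatment: about .25 SD, power 30–45%.
- Last call copied for 15 women, over a range of assumed post-treatment courses: .27 to .46 SD.
- A day-7 rating carried within condition 2 for 15 of 45: .37 with balanced orders, .29–.35 if all are on placebo second, .40–.45 if all are on active second.

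**The case against.** The strongest reply is that Section 10.3 never says values cross conditions. It could mean filling days within a condition only, and with balanced orders that costs little (.37 against .40 in the illustration). This stands as a caution: crossing is an inference. But within-condition filling cannot supply a woman with no condition-2 ratings at all, and the paired test is specified on the intent-to-treat set.

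Second, with copied means the bias is towards the null, type I error holds, power is unchanged, and no section plans a confidence interval. Section 10.4.1 expects nonparametric procedures, and a signed-rank test that drops zeros would reproduce the completers' test. All true, but the reported mean difference would still be shrunken. If a single last rating is copied, the differences are not zero and do not drop out.

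A reader might infer four stronger things that the documents do not support:
- *That d of .40 becomes d of .27.* The .27 is a mean difference in original SD units. The paired d on the filled data is about .32, because the copied zeros shrink the SD too.
- *That 15 copied women is the planned case.* Section 10.5 plans 15 non-completers. It does not say that they all finish condition 1, and its only cited attrition rate is 25%.
- *That false positives rise.* With copied means type I error stays at about 5%.
- *That the estimate will be inflated.* Inflation is possible, but its size rests on assumed symptom courses or on most losses falling in one order.

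**Conclusion.** The point holds. The plan commits its primary analysis to an undefined substitution rule, in a design that expects up to a third of randomised women not to complete. With condition-1 means copied, the estimate falls by the copied fraction: to .30 SD at 25% attrition (paired d about .35, coverage about 88%) and to .27 SD in the upper case (paired d about .32, coverage 81%). The harm is to the estimate and its apparent precision, not to the test. These figures assume an SD of the difference of 1, a true difference of .40, normal differences and completers who represent the randomised women. If a last rating is carried instead, neither direction nor size can be stated from the documents. This should be settled before unblinding.

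**What to change.** Delete the carry-forward sentence in Section 10.3. In Section 10.4.2, make the primary analysis a mixed model on each woman's condition means of observed final-seven-day ratings, with condition, period and sequence, a woman effect and small-sample degrees of freedom; use a rank-based or generalised version if the data are skewed. Include every randomised woman with at least one rating in either window. Name condition means explicitly, since a model on daily ratings weights women differently when observed days differ. Add two sensitivity analyses: completers only, and a delta-adjusted analysis for women discontinued for suicidality. State in Section 6.1.9 how the multilevel models relate to this.

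The cost is wording in three sections and slightly more analysis work, with no new data. In simulation (1,500 runs per setting, 30 completers plus 11 or 15 condition-1-only women) this model gave estimates of .39–.41 with coverage of about 95%. The downside is width: intervals are about as wide as the completers' (half-width about .37), not the falsely narrow .25.

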### 10.4 DESCRIPTION OF STATISTICAL METHODS

#### 10.4.1 GENERAL APPROACH

The design of this study is a two-period crossover design, where each of two study periods is a perimenstrual frame of the menstrual cycle (days +7 to +22 following ovulation where positive ovulation test day=0). Each participant will complete both conditions in a randomized order.

The primary windows of comparison will be the final seven days of each administration phase, which will allow for a comparison of a woman's mean scores in the placebo condition compared to her mean scores in the experimental condition.

Primary hypothesis tests will be evaluated using a alpha level of .05, with a two-tailed test.

All outcomes will be checked for normality; given the low likelihood that suicidality will follow a normal distribution even in this clinical sample, we expect that we will need to utilize nonparametric procedures.

---

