**3 OBJECTIVES AND PURPOSE**

The purpose of this mechanistic study is to experimentally test a pathophysiologic mediational model in which late luteal (perimenstrual) E2/P4 withdrawal (vs. experimental luteal E2/P4 stabilization via exogenous transdermal E2 and oral micronized P4) increases suicidal desire (via increased hopelessness and negative social appraisals) and suicidal action capacity (via reduced inhibitory control and increased threat sensitivity). We predict that natural E2/P4 withdrawal (compared to stabilization) will increase reports of suicidal desire (partially mediated by task performance indicating increased hopelessness and negative social appraisals) and action capacity (partially mediated by task performance indicating decreased inhibitory control and increased threat sensitivity).

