#### 4.2.1 PRIMARY ENDPOINT

The primary endpoints (described below) of this mechanistic study are suicidal ideation and planning score differences between placebo days and stabilization days on the SITBI interview. These were chosen given their strong predictive validity in epidemiological studies.

- (1) Mean Within-Person Condition Difference (7 final placebo days – 7 final stabilization days) of SITB Suicidal Ideation subscale score
- (2) Mean Within-Person Condition Difference (7 final placebo days – 7 final stabilization days) of SITB Suicidal Planning subscale score

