#### 10.4.9 MULTIPLE COMPARISON/MULTIPLICITY

N/A

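### Two primary endpoints are each tested at two-sided .05 with no rule for combining them, while 10.2 and 10.5 each state a single null; if either endpoint can reject it, the false-positive chance is about 8% to 10%, not 5%

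*Combined protocol and SAP*

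**What the plan says.** Section 4.2.1 lists two primary endpoints: the within-person difference in the SITB ideation subscale, and the same difference "of SITB Suicidal Planning subscale score". Section 10.4.2 applies the same analysis to every outcome in turn: a paired t-test, a repeated measures ANCOVA if covariates vary enough, or a nonparametric equivalent. On the level, 10.4.1 says: "Primary hypothesis tests will be evaluated using a alpha level of .05, with a two-tailed test".

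The section headed "10.4.9 MULTIPLE COMPARISON/MULTIPLICITY" contains only N/A. Section 10.1 says "There will be no formal SAP", so no later document is planned in which a rule could appear.

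The hypotheses are stated at two levels of detail:

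- Section 3 predicts that hormone withdrawal "increases suicidal desire (via increased hopelessness and negative social appraisals) and suicidal action capacity (via reduced inhibitory control and increased threat sensitivity". Section 2.2 says much the same, and the Protocol Summary ties ideation to desire and planning to action capacity.
- Section 10.2 states one null: "The associated null hypothesis is that there will be no difference in the perimenstrual increase in suicidality across condition".
- Section 10.5 states one null, with alpha at .05: "The null hypothesis is no link between the study experimental condition and risk for suicidal ideation, intent, and planning". It then powers one contrast for the primary hypothesis.

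**The concern.** One null, two tests at .05 each and no decision rule leave open what rejects the null. A significant result on ideation alone, on planning alone, or only on both could each be presented as the primary finding, and the choice could be made after the results are known. If either result suffices, the stated .05 applies to each test but not to the conclusion about the null in 10.2 or 10.5. If both are required, no adjustment is needed, but the protocol does not say so.

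The null in 10.5 also covers intent, which 4.2.1 does not list as an endpoint. The hypotheses and the endpoints have therefore not been matched one to one.

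**Working it through.** **Inputs.** From the protocol: two primary endpoints (4.2.1); two-sided alpha .05 per test (10.4.1); paired t-test (10.4.2); 30 completers, d = .40 and d = .60, 80% power (10.5). Assumed, because the protocol does not give them: the correlation between the two test statistics; d as the standardised paired difference; and, for power, equal effects on both endpoints.

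**1. The protocol's own figure.** Section 10.5 claims 80% power for d = .40 with 30 completers. For a two-sided paired t-test with 29 df, the noncentrality is .40 × √30 = 2.19 and power is .563. To reach 80% with 30 women, the standardised paired difference must be about .53. That follows from d = .40 between conditions if the within-person correlation is about .72: .40/√(2 × (1 − .72)) = .53. The protocol gives no such correlation. This affects only the cost in step 5, not the error rates.

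**2. Either endpoint rejects the single null.** With independent tests the error is 1 − (1 − .05)² = .0975. With correlated tests it is 1 − P(|Z₁| < 1.96 and |Z₂| < 1.96) under a bivariate normal:

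| Correlation (assumed) | False-positive chance |
|---|---|
| 0 | 9.75% |
| .3 | 9.5% |
| .5 | 9.1% |
| .7 | 8.3% |
| .9 | 7.0% |

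**3. Both endpoints required.** If both nulls are true, the error is .05² = .0025 when independent, .9% at correlation .5 and 1.7% at .7. These low rates hold only when both nulls are true. If one endpoint has a real effect, the error on the other can approach 5%. Either way it stays within .05.

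**4. Holm.** The smaller p-value is compared with .025. With both nulls true and independent tests, the chance of any rejection is 1 − (1 − .025)² = .0494. Under any correlation it is at most .025 + .025 = .05.

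**5. Cost of Holm, 30 completers.** Paired t power is .563 (d = .40) and .888 (d = .60) at .05, and .442 and .816 at .025. An endpoint is claimed if its p-value is at most .025, or if it is at most .05 and the other's is at most .025. For independent tests:

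- d = .40: .442 + (.563 − .442) × .442 ≈ .50
- d = .60: .816 + (.888 − .816) × .816 ≈ .875

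By simulation at correlation .7, the values are .494 and .860. The loss is about 7 points at d = .40 and 1 to 3 points at d = .60.

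If 30 completers really give 80% (standardised paired difference .53, step 1), power at .025 is .704. Holm then gives .704 + (.801 − .704) × .704 ≈ .77.

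If the other endpoint has no effect, the d = .40 figure is .442 + .121 × .025 ≈ .445, a loss of about 12 points.

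**The case against.** The strongest reply is that there are two hypotheses, not one. The Protocol Summary assigns each primary endpoint its own construct, sections 2.2 and 3 give each construct its own prediction and mediators, and 10.2 names both constructs just before its null. On that reading the word suicidality in 10.2 is shorthand for each in turn, and testing two distinct hypotheses at .05 each is a recognised position. The protocol also says that it is mechanistic, not an efficacy trial, so two results may simply be reported side by side with no overall claim.

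This stands in part. It shows that the inflated error belongs to one reading and not to the plan as a certainty. It does not remove the gap: 10.2 and 10.5 each state a single null, 10.5 powers a single contrast, and N/A does not declare two separate families. A team that wants separate .05 claims would still have to rewrite those sections.

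On intent, the eligibility table numbers the SITBI intent item alongside the planning items, so intent may belong to the planning score. The documents do not settle this, so the mention needs reconciling rather than deleting.

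The power figures use 30 completers, whereas 10.3 plans an intent-to-treat analysis with carry-forward and 10.5 randomizes 45. The power cost would change with the number analysed; the error rates in steps 2 to 4 would not.

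**Conclusion.** The point holds as a missing decision rule. Two primary tests at .05 face a single stated null, and nothing says whether one or both must succeed. If either suffices, the false-positive chance is 9.75% for independent tests, 9.1% at correlation .5 and 8.3% at .7, against a stated .05. The correlations are assumptions.

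Three stronger conclusions are tempting, and the documents do not support them:

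- That the trial's error rate simply is 9.75%. No section adopts the either-endpoint rule, and 10.4.1 promises no family-wise rate.
- That planning will sit at the floor because 5.1 excludes recent concrete planning. The documents give neither the scoring of the daily planning subscale nor the expected share of women with a non-zero difference. Section 10.4.1 says only that suicidality is unlikely to be normally distributed and that "we expect that we will need to utilize nonparametric procedures".
- That planning should be tested only after ideation succeeds. With 30 completers and d = .40 on both endpoints, that order would cut planning's chance of a claim from 56% to 32% (.563², independent tests) or 44% (correlation .7). It would also subordinate half of a two-part model.

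**What to change.** Settle the rule before unblinding.

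1. In 10.4.9, replace N/A with: *The two primary endpoints are tested with Holm's procedure at a family-wise two-sided .05: the smaller p-value is compared with .025 and, if significant, the other with .05. If the smaller is not significant, neither endpoint is claimed.* This works with the paired t-test, the ANCOVA or a nonparametric test.
2. In 10.2 and 10.5, replace the single null with two, one for ideation and one for planning, each stated on the seven-day mean difference defined in 4.2.1.
3. In 10.5, reconcile intent with the endpoint list: say which endpoint contains it, or take it out of the null.

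The change is wording only and leaves eligibility, visits, sample size and the tests themselves as they are. The price is the loss of power per endpoint worked out above: about 7 points at d = .40 and 1 to 3 at d = .60 if both effects are equal, and about 12 points at d = .40 if the other endpoint has no effect.
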